6.1. Subject Enrollment

TRACE is anticipated to enroll approximately 250 subjects at approximately 10 sites who have undergone cryoablation of a renal lesion via a Galil Medical cryoablation system using Galil Medical needles. Subjects will be enrolled from a mix of academic and community-based physician sites.

To minimize selection bias within the enrolled subject population, participation in the registry is to be offered to all eligible patients on a consecutive basis as they present to the physician at each site. A log of eligible but non-enrolling patients will also be maintained. The log will include minimal health information regarding each non-enrolling patient (e.g., age, gender, reason for not enrolling) and will enable the evaluation of potential selection bias at periodic intervals throughout conduct of the registry. As the non-enrolled patients will not sign an informed consent form, their log data will be assigned an anonymous identifier and the data collected will not include personally identifiable information (as defined in 45 CFR 164.514).

6.2. Inclusion Criteria

Patients are required to meet all of the following criteria to be eligible for participation in the registry:

1. Patient is at least 18 years of age.
2. Patient has a renal lesion suspicious for malignancy.
3. Patient is to undergo renal lesion cryoablation via a Galil Medical cryoablation system using Galil Medical needles for treatment of primary or recurrent disease.
4. Patient is to be available for long-term follow-up per the enrolling physician's standard care practices.
5. Patient has provided written informed consent.

6.3. Exclusion Criteria

Patients who meet the following exclusion criteria are not eligible for enrollment in the registry:

1. Patient is either currently using or has used within the last 30 days an investigational product of any type.
2. Patient has metastatic disease to or from the kidney.

3. Patient has had previous therapy on the index lesion (e.g. radiofrequency, cryoablation, partial nephrectomy).

6.4. Renal Lesion Size

There are no strict exclusion criteria with regard to lesion size. The typical renal lesion suitable for cryoablation is ≤ 4 cm, however, as TRACE is an observational study of the real-world outcomes of cryoablation surgery using Galil Medical products, physicians are to use their training and experience to determine the size of a renal lesion that is appropriate for cryoablation.

6.5. Withdrawal of Subjects

Subjects may withdraw from the registry at any time, with or without reason and without prejudice to further treatment. As possible, the reason(s) for withdrawal (if given) will be recorded.

The remainder of this page is intentionally blank

7. Registry Assessments

The following table summarizes the data to be collected for each subject over the course of his/her TRACE participation.

Table 1: Registry Event Schedule

	Initial Collection of Data	Cryoablation Data	Subsequent Visit(s) Based Upon Site Standard of Care
Enrollment Date	X		
Informed Consent Obtained	X		
Demography	X		
Comorbidities	X		
Medical History	X		
Concomitant Medications	X		X
Imaging (Baseline)	X		
Quality of Life (SF-12)	X		X (6 & 12 mo)
Pre-Cryo Biopsy	X (if available)		
Pre-Cryo Pathology	X (if available)		
Intra-operative Biopsy		X (if available)	
Intra-operative Pathology		X (if available)	
Cryotherapy Procedure		X	
Intra-operative Complications		X	
Hospital Stay		X	X
Clinical Laboratories	X	X (if available)	X
Post-operative Complications		X	X
Post-operative Interventional Treatment		X	X
Follow-Up			X
Imaging Follow-up			X
Biopsy Follow-up			X (if available)
Pathology Follow-up			X (if available)
Primary Lesion Recurrence			X
New Renal Lesion Emergence			X
Emergence of new neoplastic disease (any type)			X
Development of metastatic disease			X
Withdrawal			X

7.1. Pre-Cryoablation Evaluation

Subjects will be enrolled in TRACE during their pre-cryoablation visit. The registry will collect data on the lesion characteristics, selected procedural parameters, associated safety measures, and short- and long-term clinical outcomes of the cryoablation procedure. The following information will be collected on all subjects entering the registry:

A. Data to be Collected by the Investigator and/or Study Coordinator

- Demographics (e.g., date of birth, gender, ethnicity)
- Height and weight
- ASA Classification
- Comorbidities (e.g., diabetes, hypertension, obesity, clotting disorder)
- Present Medical history
 - Incidental or symptomatic finding
 - Renal status
 - Previous renal surgery / History of suspicious lesion
- Cancer(s) other than renal
- Pertinent medication classes
- Smoking history
- Baseline Imaging
 - Type of imaging
 - Number of lesions identified (measures for each lesion should be recorded separately)
 - Lesion location: anterior, lateral, posterior, upper pole, mid-segment, lower pole, medial, hilar (within 5 mm of the renal hilum), with the following classification of the percentage of the mass that extends into the normal renal parenchymal border⁶
 - Exophytic- <40%
 - Mesophytic-40-60%
 - Endophytic- more than 60%
 - Lesion size measured by two methods:
 - 1) 3-dimensional measurements (cm) and
 - 2) Greatest trans-axial diameter (cm)
 - Lesion shape (spherical or non spherical)
 - Nephrometry Score
 - Hounsfield units
- Pre-Cryo Biopsy (if available)
 - Date
 - Type of biopsy (FNA or Core)
 - Number of cores taken
- Pre-Cryo Pathology (if available)
 - Classification of Lesion
 - Fuhrman Grade

- Clinical Laboratory Assessments (if available)
 - Creatinine
 - Estimated Glomerular Filtration Rate (eGFR)⁵
 - CBC (WBC, HCT, Hgb, Platelet)
 - BUN
 - LFT
 - PT
 - PTT

B. Baseline Quality of Life Questionnaire

Enrolled subjects will complete the Short Form-12 (SF-12) during the office visit. The SF-12 is a brief (twelve-item) health status survey to monitor outcomes in general and specific populations.

7.2. Cryoablation Procedure

The following data should be collected prior to or at the time of the procedure, as available.

- Procedure method (open, laparoscopic, percutaneous)
- Number of lesions treated with cryoablation
- Type of hemostatic agents or maneuvers used
- Lesion size measured by two methods:
 - 1) 3-dimensional measurements (cm) and
 - 2) Greatest trans-axial diameter (cm)
- Intra-operative biopsy (if available)
- Intra-operative pathology (if available)
- Hospital Stay
- Clinical laboratories (if available)
- Lesion location: anterior, lateral, posterior, upper pole, mid-segment, lower pole, medial, hilar (within 5 mm of the renal hilum), with the following classification of the percentage of the mass that extends into the normal renal parenchymal border⁶
 - Exophytic- <40%
 - Mesophytic- 40-60%
 - Endophytic- more than 60%
- Lesion shape (spherical or non spherical)
- Pathology of the lesion (if available)
- Number and type of cryosurgery needles used
- Number of freeze and thaw cycles
- Freeze and thaw times, per cycle
- Lowest temperature achieved at end of each freeze cycle
- Hilar clamping
- Embolization

- Galil needle cautery
- Method of thaw (active or passive)
- Method of monitoring iceball formation (US, CT, MRI)
- Involvement of the kidney's collecting system
- Post-operative HCT

7.3. Early Complications

The following data should be collected at the time of the procedure, or prior to discharge as applicable:

- Number and type of intra-operative complications
- Severity of complications
- Requirement for hospital admittance/stay
- Requirement for surgical intervention(s)

7.4. First Post-Operative Follow-Up

The following data should be collected at the first post-operative follow-up:

- Potentially related or directly related cryoablation adverse events
- Surgical intervention(s), as applicable

7.5. Ongoing Follow-Up Visits

It is anticipated that each subject will be seen at least once per year for a follow-up check-up.

The following follow-up data, as available, will be collected for each subject:

- Potentially related or directly related delayed cryoablation adverse events
- Lab assessments (creatinine, estimated GFR)
- Imaging results
- Biopsy/pathology results if available
- Assessment of disease progression, including retreatment
- Emergence of a new renal lesion
- Emergence of new neoplastic disease (any type)
- Emergence of metastatic disease
- Quality of Life Assessment (SF-12) at 6 and 12 months post procedure

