At the first post-cryoablation visit, data regarding initial outcomes and potentially or directly related complications, as applicable, will be collected, as will details regarding any post-operative interventional treatments. Data collection for subsequent follow-up visits will address delayed potentially or directly related complications, ongoing imaging and biopsy procedures as well as the introduction and continued use of new cancer treatments.

The schedule and number of follow-up visits for each subject will be determined by his/her physician's standard of care. Within this context, semi-annual to annual follow-up during the five-year follow-up period is generally anticipated though it is recognized that follow-up schedules will vary among enrolled subjects. The subject will be asked to complete the quality of life questionnaire post-cryoablation at the 6 and 12 month follow-up intervals if scheduled.

All potentially related and directly related cryoablation adverse events (AEs), serious adverse events (SAEs) and unanticipated adverse device effects (UADEs) that occur within 30 days after

the cryoablation procedure is performed will be recorded. The cryoablation AEs, SAEs, and UADEs identified within the first 30 days after the cryoablation procedure will be followed and reported until resolution or for a period of 6 months.

Concomitant medications may be prescribed as per the physician's standard of care while the subject is participating in the registry. Only classes of concomitant medications will be collected at each follow-up visit.

6. Registry Population

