10.1. Monitoring and Auditing

Participating TRACE sites will be managed remotely via regular telephone contact and, as necessary, on-site monitoring visits; no routine monitoring visits will be conducted. When necessary, site visits will be performed by an authorized representative from Galil and will be conducted according to applicable GCP and local regulatory guidelines.

In addition, sites may be subject to an audit visit by Galil or a local regulatory authority (e.g., FDA). If such a site audit occurs, the investigator agrees to provide access to all pertinent subject records, eCRFs and other site documents deemed necessary to complete the audit visit.

By signing the Registry Agreement, the investigator grants permission to authorized representatives of Galil and/or local regulatory authorities to conduct on-site monitoring visits for the purpose of reviewing the collected registry data and to review site procedures employed in the conduct of TRACE.

11. Adverse Events

All potentially related and directly related cryoablation adverse events (AEs), serious adverse events (SAEs) and unanticipated adverse device effects (UADEs) that occur within **30 days after the cryoablation procedure** is performed will be recorded. The cryoablation AEs, SAEs, and UADEs identified within the first 30 days after the cryoablation procedure will be followed and reported until resolution or for a period of 6 months.

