6 BASELINE, EFFICACY AND SAFETY EVALUATIONS

6.1 Schedule of Evaluations

The following table summarizes the data to be collected for each patient over the course of his/her participation in the TRACE study.

Table 2 Event schedule

	Initial Collection of Data	Cryoablation Data	Subsequent Visit(s) Based Upon Site Standard of Care
Enrollment Date	X		
Informed Consent Obtained	X		
Demography	X		
Comorbidities	X		
Medical History	X		
Concomitant Medications	X		X
Imaging (Baseline)	X		
Quality of Life (SF-12)	X		X (6 & 12 mo)
Pre-Cryo Biopsy	X (if available)		
Pre-Cryo Pathology	X (if available)		
Intra-operative Biopsy		X (if available)	
Intra-operative Pathology		X (if available)	
Cryotherapy Procedure		X	
Intra-operative Complications		X	
Hospital Stay		X	X
Clinical Laboratories	X	X (if available)	X
Post-operative Complications		X	X
Post-operative Interventional Treatment		X	X
Follow-Up			X
Imaging Follow-up			X
Biopsy Follow-up			X (if available)
Pathology Follow-up			X (if available)
Primary Lesion Recurrence			X
New Renal Lesion Emergence			X
Emergence of new neoplastic disease (any type)			X
Development of metastatic disease			X
Withdrawal			X

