6.5.2 Adverse Events

Intra-operative device complications will be recorded, and whether or not the complication was related to the malfunction of the cryoablation system. Intra-operative patient complications will also be recorded.

All potentially related and directly related cryoablation adverse events (AEs), serious adverse events (SAEs) and unanticipated adverse device effects (UADEs) that occur within 30 days after the cryoablation procedure will be recorded.

The investigators will use the National Cancer Institute (NCI) Common Toxicity Criteria for Adverse Events [CTCAE] (version 3.0) grading system, and also the Clavien classification. AE terms will be selected from a pre-specified code list within the eCRF, and will be auto-coded within the eCRF using the CTCAE Short Term.

The incidence of AEs will be the number of patients who had the AE (counted only once) divided by the number of patients in the analysis population and represented as a percentage.

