8.7.2 Adverse Events

The number and percentage of patients with the following complications will be given, together with 95% CIs for the percentages, computed using the method of Wilson (1927):

- Intra-operative device complication
- Intra-operative device complication related to the malfunction of the cryoablation system cryosurgery
- Intra-operative patient complication

AEs will be summarized by the code list provided in the eCRF in descending order of frequency; a patient will only be counted once per code. Patient counts and percentages (and 95% CIs) and event counts will be presented for the following summaries.

- Overall summary of AEs, including
 - total number of AEs, SAEs, UADEs
 - total number of AEs, SAEs, UADEs by the following subgroups:
 - CTCAE grade
 - Clavien classification
 - Site
 - Procedure method
 - NS complexity category at baseline (as defined in Section 6.3)
 - ASA score
 - Baseline lesion classification (i.e., exophytic, mesophytic, endophytic); AEs for patients with multiple lesions with different classifications will be in a separate category.
 - Did iceball appear to touch the collection system?
 - Comorbidities (HIV/immunocompromised; diabetes; hypertension; obesity; blood clotting disorder; abdominal surgery; cardiovascular; retroperitoneal surgery; von Hippel-Lindau; cancer, other than renal)
- All AEs
- All AEs by CTCAE grade
- All AEs by baseline lesion classification (i.e., exophytic, mesophytic, endophytic); AEs for patients with multiple lesions with different classifications will be in a separate category
- All AEs by the comorbidities listed above
- All SAEs
- All UADEs
- All AEs with CTCAE grade ≥ 3
- All fatal AEs (CTCAE grade 5).

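### The 30-day limit on recording related adverse events conflicts with the collection of delayed events, and the SAP's AE incidence, tables and regression do not apply it

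*Protocol*

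**What the plan says.** Three places set a 30-day limit on what is recorded:

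- Protocol 5.1 covers "All potentially related and directly related cryoablation adverse events (AEs), serious adverse events (SAEs) and unanticipated adverse device effects (UADEs) that occur within 30 days" of cryoablation, and the opening of Protocol Section 11 repeats the sentence.
- SAP 6.5.2 takes the same rule over: related events "that occur within 30 days after the cryoablation procedure will be recorded".
- Events found in that period "will be followed and reported until resolution or for a period of 6 months" (Protocol 5.1 and Section 11).

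Other places ask for later events or set no limit:

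- Protocol 5.1, on visits after the first: "Data collection for subsequent follow-up visits will address delayed potentially or directly related complications".
- Protocol 7.5 lists "Potentially related or directly related delayed cryoablation adverse events" among the data for ongoing visits, which are expected at least yearly over five years.
- The event schedules (Protocol Table 1, SAP 6.1) mark "Post-operative Complications" under subsequent visits as well as under the cryoablation column.
- Protocol 11.1 defines an AE without a time limit and requires every AE to be entered in the database. Protocol 11.3 requires any related SAE or UADE to be reported, also without a limit.

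On analysis, SAP 6.5.2 states: "The incidence of AEs will be the number of patients who had the AE (counted only once) divided by the number of patients in the" population analysed. SAP 8.7.2 adds that "AEs will be summarized by the code list provided in the eCRF in descending order of frequency", with many subgroup splits but none by onset time. The logistic regression in SAP 7.2 models whether an AE occurred, with no window.

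**The concern.** A site could follow either set of instructions and be in line with the protocol. One that stops at 30 days and one that enters AEs at each yearly visit would contribute to the same percentage.

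The AE percentage is the registry's main safety result, and the primary objective covers both short- and long-term outcomes. The anticipated-event list in Protocol 11.1 includes stricture, ureteropelvic junction obstruction, urinary fistula and renal failure, which may appear late. AEs are tabulated by site and procedure method, surgical approach is a covariate in the AE regression, and comparing outcomes across approaches is a secondary objective. If late capture differed between sites, those comparisons could partly show who recorded late events rather than who had them.

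Such a difference would be hard to detect. Protocol 10.1 plans no routine monitoring visits and SAP 8.2 does not record protocol deviations. SAP 8.6.10 omits a poolability assessment because outcome assessment is expected to be common to all sites.

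**Working it through.** The documents state no AE rate, so there is no figure to reproduce. The check is a comparison of text, followed by an illustration on assumed inputs.

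**1. Does another rule reconcile the passages?** The 6-month rule does not: it concerns events already identified within 30 days and opens no window for new ones. SAP 5.2, which lists departures from the protocol, does not mention delayed AEs.

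**2. Is the window applied in the analysis?**

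| Element | Onset window | Time at risk |
|---|---|---|
| Recording rule, SAP 6.5.2 | 30 days | not applicable |
| Incidence formula, SAP 6.5.2 | none stated | none; whole analysis population |
| Tables, SAP 8.7.2 | none stated | none |
| Logistic regression, SAP 7.2 | none stated | none |

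The limit appears only as a recording rule. No analysis text says what happens to a delayed AE that is in the database.

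**3. How far could the choice of window move the percentage?** Inputs: N = 250 (Protocol 8.1, SAP 4.4). Assumed: 25 patients with an AE by day 30, and 0 to 25 further patients whose first AE comes later. The interval is Wilson's, which SAP 8.7.2 names for the complication percentages:

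[p + z²/(2n) ± z·√(p(1−p)/n + z²/(4n²))] / (1 + z²/n), with z = 1.96.

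For 25/250: (0.1000 + 0.0077 ± 1.96 × 0.01937) / 1.01537 = 0.069 to 0.143.

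| Later first AEs | Patients with an AE | Percentage (95% CI) |
|---|---|---|
| 0 | 25 | 10.0% (6.9 to 14.3) |
| 5 | 30 | 12.0% (8.5 to 16.6) |
| 12 | 37 | 14.8% (10.9 to 19.7) |
| 25 | 50 | 20.0% (15.5 to 25.4) |

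**4. What does the fixed denominator do to late events?** Assume a true five-year late-AE risk of 5% with constant hazard h = −ln(0.95)/5 = 0.01026 per year, and exponential dropout reaching share d by year 5, so c = −ln(1−d)/5. The crude percentage is h/(h+c) × [1 − exp(−5(h+c))]. For d = 40%, c = 0.10217 and the result is 0.01026/0.11242 × (1 − 0.95 × 0.60) = 3.9%. For d = 0, 20% and 60% it is 5.0%, 4.5% and 3.3%. Late events would therefore be understated, and more so as dropout rises.

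**5. Can the two sets be separated?** Yes. Onset date is recorded (Protocol 11.2), partial dates are not permitted (SAP 6.2.1.1), and relative days are already calculated for safety endpoints (SAP 6.2.1).

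**The case against.** The best defence is that the window is there to be read. SAP 6.5.2 states the 30-day limit and defines incidence in the same subsection, and SAP 8.7.2 analyses the variable defined there. Section 11 of the protocol emphasises the 30-day phrase, and all sites are trained on data collection (Protocol 9.1). For a 30-day incidence, a whole-population denominator is a normal choice. Late renal decline is followed separately through eGFR, creatinine and CKD stage (SAP 8.8.4). Listings of all eCRF data are planned (SAP 7.1), so late events would be visible. Table shells are in a separate document and may state the window. The registry is descriptive and has no AE threshold to meet.

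Most of this stands. A 30-day window can be inferred, so it would be too strong to say that the AE incidence has none. What remains is that the inferred limit is a recording rule, that other protocol text contradicts it, and that the analysis text neither applies it nor says how a later event is handled. Renal function tables do not cover stricture, obstruction or fistula. Listings show late events but do not keep them out of the percentage.

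**Conclusion.** The inconsistency is real and should be resolved: a 30-day window is stated for recording, contradicted by delayed-event collection and by untimed AE and SAE rules, and not carried into the analysis. The consequence is conditional on at least one AE with onset after day 30 being entered. Its size cannot be derived from the documents. The 0 to 10 percentage-point range in the working rests wholly on the assumed rates.

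Two stronger readings are tempting and not supported:

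- A reader might infer that the reported percentage will be a mixture and that comparisons by site or approach are distorted. Nothing in the documents shows that late AEs are in the database or that sites differed, and the eCRF instructions are not available. Both effects are possible, not established.
- A reader might infer that the 30-day rule understates the AE rate: if 10% to 30% of affected patients had their AE only after day 30, a 10% any-time rate would show as 10% × 0.9 = 9% to 10% × 0.7 = 7%. Those inputs are assumptions. A 30-day incidence and an any-time incidence are both valid quantities, so their difference is not bias and does not measure mixing.

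**What to change.** 1. Reconcile Protocol 5.1, 7.5, 11, 11.1, 11.3 and the event schedules on the recording window, and state in SAP 5.2 what sites were asked to record.
2. In SAP 6.5.2 and 8.7.2, define the AE incidence as onset within 30 days after the procedure and label it 30-day incidence. Apply the same definition to the AE outcome in the SAP 7.2 logistic regression. Give the cut in relative days: because SAP 6.2.1 makes the procedure date day 1, 30 days after it is relative day 30 + 1 = 31.
3. Report any AE, SAE or UADE with later onset in a separate table of counts, labelled incompletely ascertained, and keep it out of that percentage.

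No new data are needed. The cost is SAP wording, one derived flag and one extra table. The main table may show a lower overall AE count than an all-onset table would. If no later event is found, the extra table is empty and the percentages do not change.
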